##### Progression-free survival (PFS)

- Time to event

Time to progression is defined by a composite endpoint. At the end of the treatment epoch, the Kaplan-Meier estimates of the proportion of participants who are still at the risk , along with 80% two-sided confidence intervals using Greenwood's formula, will be provided if sufficient data is available. In addition, the Kaplan-Meier estimates will be plotted against time.

The composite endpoint including ANY of the following events:

- Absolute reduction from baseline of  $\geq 10\%$  predicted in FVC
- Non-elective hospitalization for respiratory events
- Lung transplant
- Death

Non-elective respiratory hospitalizations will be defined as any unplanned inpatient hospitalizations for which the primary cause was a pulmonary condition, in the opinion of the blinded adjudicators and based on all available clinical data. Examples include, but are not limited to, the following:

- acute exacerbation of IPF (definite or suspected)
- pulmonary infection/pneumonia -pulmonary embolus
- pneumothorax
- -ulmonary aspiration
- ARDS of identifiable cause

Individual components of the composite endpoint will be summarized separately and if sufficient data is available, then further appropriate statistical analyses will be conducted.

- Progression rate

The event rates for composite endpoint and each individual components (i.e. including absolute decline of  $\geq 10\%$  predicted in FVC) between the treatment group and the placebo group will be compared using logistic regression model if enough the data allows.

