12.5 Analysis supporting secondary objectives

12.5.1 Efficacy and/or Pharmacodynamic endpoint(s)

Efficacy

Change from baseline to end of treatment epoch (26 weeks of treatment) in Forced Vital Capacity (FVC) expressed in mL will be analyzed using a similar model stated in [Section 12.4.2](#) with both treatment and placebo group using non-informative prior.

Summary statistics of change from baseline in FVC by visit and treatment will be presented.

Progression-free survival (PFS)

Time to progression is defined by a composite endpoint. At the end of the treatment epoch, the Kaplan-Meier estimates of the proportion of participants with the composite endpoint, along with 80% two-sided confidence intervals using Greenwood's formula, will be provided. In addition, the Kaplan-Meier estimates will be plotted against time.

The composite endpoint including ANY of the following events:

- Absolute reduction from baseline of $\geq 10\%$ predicted in FVC
- Non-elective hospitalization for respiratory events
- Lung transplant
- Death

Individual components of the composite endpoint will be summarized separately and if sufficient data is available, then further appropriate statistical analyses will be conducted.

Incidence of absolute decline in FVC $\geq 10\%$ predicted

Binary output of absolute decline of $\geq 10\%$ predicted in FVC (Yes/No) at the end of treatment epoch (26 weeks of treatment) will be assessed using logistic regression model with absolute decline of $\geq 10\%$ (Yes/No) as dependent variable, and the treatment as explanatory variable. Baseline FVC%^{op} and use of background therapy may be included as potential covariates. The estimated rate of the absolute decline of $\geq 10\%$ predicted in FVC by treatment group and the difference between the treatment and the placebo group will be presented together with 90% confidence intervals.

The number and percentage of participants with absolute decline of $\geq 10\%$ predicted in FVC will be presented by epoch/visit and treatment.

Pulmonary physiology

To assess the impact of the IPs on pulmonary physiology, change from baseline to the end of treatment epoch (26 weeks of treatment) in DLCO will be analyzed by fitting the same model as described for the primary endpoint in [Section 12.4.2](#) with non-informative priors on both treatment arms in addition to summary statistics by treatment.

Exercise capacity

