## 1.2 Study objectives, endpoints and estimands

**Table 1-1 Objectives and related endpoints**

| Objective(s)   | Endpoint(s)  |
|--|--|
| Primary objective(s)  | Endpoint(s) for primary objective(s)  |
| 

To assess the efficacy of the investigational products compared to placebo in participants with IPF

  | 

Change from baseline to end of treatment epoch (26 weeks of treatment) in Forced Vital Capacity (FVC) expressed in percent predicted

   |
| Secondary objective(s)  | Endpoint(s) for secondary objective(s)  |
| 

To assess the efficacy of the investigational products, compared to placebo in participants with IPF

To assess the impact of the investigational products on "progression-free survival (PFS)"

To assess the incidence of absolute decline in FVC <math>\geq 10\%</math> predicted

To assess the impact of the investigational products on pulmonary physiology

To assess the impact of the investigational products on exercise capacity

To assess the impact of the investigational products on patient reported outcome

To assess the safety and tolerability of the investigational products in participants with mild to moderate IPF

 | 

Change from baseline to end of treatment epoch (26 weeks of treatment) in Forced Vital Capacity (FVC) expressed in mL

Time to progression as defined by a composite endpoint including any of the following events:

Absolute reduction from baseline of <math>\geq 10\%</math> predicted in FVC

Nonelective hospitalization for respiratory events

Lung Transplant

Death

Number of participants with absolute decline of <math>\geq 10\%</math> predicted in FVC

Change from baseline to the end of treatment epoch (26 weeks of treatment) in DLCO absolute and percent predicted

Change from baseline to the end of treatment epoch (26 weeks of treatment) in 6-minute walk distance

Change from baseline to the end of treatment epoch (26 weeks of treatment) in scores from the L-IPF (Impacts and Symptoms Modules), K-BILD, Leicester cough, and R-Scale for PF questionnaires

Adverse Events, physical examinations, labs, ECGs, vital signs

 |

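### SAP 2.6.1.1 makes the between-arm comparison for FVC decline of at least 10% predicted conditional on an undefined criterion and omits the protocol's arm rates and difference with 90% CIs

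*SAP*

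**What the plan says.** Both documents list this endpoint separately from PFS. SAP Table 1-1 keeps the objective "To assess the incidence of absolute decline in FVC" of at least 10% predicted, with the endpoint "Number of participants with absolute decline of" that size.

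Protocol 12.5.1 gives it its own heading. The binary outcome "predicted in FVC (Yes/No) at the end of treatment epoch (26 weeks of treatment) will be assessed using logistic regression model", with treatment as explanatory variable; baseline FVC%p "and use of background therapy may be included as potential covariates". The estimated rate in each arm and "the difference between the treatment and the placebo group will be presented together with 90% confidence intervals". Numbers and percentages by visit are added. None of this depends on how much data there is, and no interval method is named.

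SAP 2.6.1.1 has no heading for the endpoint. It is named in a parenthesis under PFS, in the item on progression rate, where rates for the composite and each component "will be compared using logistic regression model if enough the data allows". That item states no time point, arm rates with intervals, rate difference, confidence level, criterion for enough data or fallback. It names no covariates, although the general rule in SAP 2.1 would bring in the stratification factor. Just before it, the SAP says "Individual components of the composite endpoint will be summarized separately", without saying which statistics.

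SAP section 4 lists four departures from the protocol: placebo pooling, sensitivity and supplemental analyses of the primary endpoint, exploratory analyses, and interim analyses. This one is not among them.

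**The concern.** The protocol fixes in advance what will be reported for this endpoint. Under the SAP, whether any between-arm comparison appears depends on a later judgement with no stated rule. If the judgement is negative, or the model is run and an arm has no events, the SAP provides neither an effect estimate nor an interval.

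That is most likely when events are few. Early termination may add to this, though the documents do not give the number analysed. A reader comparing the report with the protocol would find a declared analysis missing and no explanation in the section meant to explain changes.

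**Working it through.** The documents give no event rate, power or sample size for this endpoint (protocol 12.8.2 marks secondary endpoints as not applicable), so there is no planned figure to reproduce. As a check on arm size, 40/(1 - 0.15) = 47.06, which agrees with the 47 per arm in protocol 17.1.11.1.

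**Inputs from the documents.** Placebo mean change at week 26 of -3 points (protocol 12.4.2); design effect 2 points, SD about 5, 40 evaluable per arm (protocol 12.8.1); 47 randomized per arm (protocol 17.1.11.1).

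**Assumptions.** Week-26 change is normally distributed, with one value per participant. SDs of 4 and 6 and arms of 20 and 30 are illustrative.

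**Event rates.** P(decline of at least 10 points) = Φ((-10 - mean)/SD).
- Placebo: Φ(-7/5) = 0.081, or 3.2 events expected in 40.
- Active (mean -3 + 2 = -1): Φ(-9/5) = 0.036, or 1.4 events expected in 40.

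**Chance of an empty arm.** P(no events in an arm) = (1 - p)^n. At n = 40 this is 3.4% for placebo and 23.1% for active. P(at least one empty arm) = 1 - (1 - 0.034)(1 - 0.231) = 0.26.

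| n per arm | SD 5, effect 2 | SD 5, no effect | SD 4, effect 2 | SD 6, effect 2 |
|---|---|---|---|---|
| 47 | 19.5% | 3.8% | 62.5% | 4.1% |
| 40 | 25.8% | 6.8% | 68.7% | 6.8% |
| 30 | 38.7% | 15.4% | 78.2% | 14.3% |
| 20 | 57.7% | 33.7% | 87.8% | 30.7% |

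With assumed rates of 10% and 5% instead, the figures are 14% at 40 per arm, 25% at 30 and 44% at 20.

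**What the model does with an empty arm.** Take placebo 3/40 and active 0/40. Newton steps for the maximum-likelihood log odds ratio give -3.7 (SE 3.6) after 5 steps, -8.7 (SE 43) after 10 and -18.7 (SE 6355) after 20. It does not converge.

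**What a direct calculation gives on the same data.** The 90% Wilson intervals are 3.0% to 17.3% around 7.5% for placebo, and 0% to 6.3% around 0% for active. Newcombe's interval for the difference of -7.5 points combines them:
- lower limit: -7.5 - √(0² + (17.3 - 7.5)²) = -17.3;
- upper limit: -7.5 + √(6.3² + (7.5 - 3.0)²) = +0.2.

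A Firth penalty also gives a finite value. In this two-group case it amounts to adding one half to each cell: log[(0.5/40.5)/(3.5/37.5)] = -2.02.

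**The case against.** A reader might infer that the SAP swapped the protocol's analysis for a logistic regression. It did not: protocol 12.5.1 already prescribes that model.

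A reader might also infer that the SAP created the empty-arm problem. It did not. The protocol presents its rates and difference straight after the logistic model and names no interval method. If they come from that model, they meet the same difficulty: in the treatment-only model an empty arm contributes variance p(1 - p)/n = 0, so its interval collapses. The SAP's condition, though undefined, at least acknowledges sparse data.

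A third tempting reading is that the endpoint would go unreported. The SAP still plans a separate summary of the components. Counts per arm may well appear, and a crude difference then follows by subtraction. What is no longer promised is the difference as an estimate, its interval, and the week-26 time point.

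The probabilities depend heavily on assumptions. They also use week-26 rates, whereas the SAP gives no time point. If any visit counted, an assumed trajectory model (slope SD 4.0, residual SD 2.1, neither from the documents) gives rates of about 9.8% and 4.6%. The empty-arm chance is then about 17% at 40 per arm and 12% at 47. The objectives tables give no time point for this endpoint either; only protocol 12.5.1 does.

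Finally, SAP 1.2.1 describes the study as phase IIa and not registrational, and this endpoint cannot change the primary conclusion. All of this stands. It limits the point's weight but does not restore the omitted estimates or supply the missing rule.

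**Conclusion.** The point holds as a gap between SAP and protocol. The SAP keeps the logistic regression but makes it conditional on an undefined criterion. It drops the week-26 arm rates and their difference with 90% intervals, names no fallback for an empty arm, and leaves the change out of section 4. The documents do not support saying that the SAP replaced the method, introduced the zero-event weakness, or abandoned the endpoint.

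The chance of an empty arm is about 20% to 26% at the planned size under the design inputs. At 40 per arm it ranges from 7% to 69% as the SD goes from 6 to 4, and is 7% with no effect. With assumed smaller arms after early termination (SD 5, effect 2) it is 39% at 30 and 58% at 20. All of these rest on normality of the week-26 change. The omission itself rests on no assumption; it follows from the texts. The correction is worth making because it is cheap and a direct rate difference exists for any event count.

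**What to change.** Give the endpoint its own paragraph in SAP 2.6.1.1. Report the rate in each arm and the active-minus-placebo difference at the end of the treatment epoch, with a 90% interval that is valid with zero cells (for example Miettinen-Nurminen or Newcombe), whatever the event count. Add counts and percentages by visit, as in protocol 12.5.1. Keep the logistic model as supportive, with a Firth or exact fallback when an arm has no events, and drop or define the condition on enough data. List any remaining departure from protocol 12.5.1 in SAP section 4.

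The cost is one paragraph and one table. The downside is that the direct interval is not adjusted for the protocol's optional covariates; the supportive model can carry those where it can be fitted.

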9.5 Early study termination by the sponsor

The study can be terminated by Novartis at any time.

Reasons for early study or cohort termination may include but are not limited to:

- Unexpected, significant, or unacceptable safety risk to participants enrolled in the study
- Decision based on recommendations from applicable board(s) after review of safety and efficacy data
- Discontinuation of study drug development

In taking the decision to terminate, Novartis will always consider participant welfare and safety. Should early termination be necessary, participants must be seen as soon as possible for an EOT visit and enter into the safety follow-up period as per their respective cohort. The investigator may be informed of additional procedures to be followed in order to ensure that adequate consideration is given to the protection of the participant's interests. The investigator or sponsor depending on local regulation will be responsible for informing IRBs/IECs of the early termination of the trial.

10 Safety monitoring, reporting and committees

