### 1.1 Study design

[figure not shown]
This is a randomized, placebo-controlled, participant- and investigator-blinded platform study in participants with IPF.

This study uses a platform type design to investigate “multiple targeted therapies in the context of a single disease in a perpetual manner” (Woodcock and LaVange 2017). Each investigational product and matching placebo entered the trial at a given time will be considered a unique cohort. The decision to include future cohorts is not dependent on performance of prior investigational products or cohorts. Each time a new cohort is introduced, investigational product specific information will be added to the protocol (Protocol Section 17) as a substantial amendment and submitted to Health Authorities and Ethical Committees, as required by local regulations. The cohort specific analysis will be added into an SAP amendment accordingly where necessary.

If multiple cohorts are open, participants will be allocated based on the cohort-specific eligibility criteria. Should a participant be eligible for more than one cohort, they will be randomized to any suitable cohort.

For each completed cohort, the data analysis will be performed upon final database lock for the cohort, and the results will be reported upon completion of each cohort in an end of cohort report. In general, each cohort in the study will undergo similar study evaluations and assessments. Each cohort will include a screening period (Day -42 to Day -1), a treatment period of 26 weeks (Day 1 to Day 183), and a post treatment safety follow-up that is cohort specific per Protocol Section 17.

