#### **2.6.3 Handling of missing values/censoring/discontinuations**

Missing data will not be imputed.

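### The only named between-arm comparison of the time-to-progression composite is a logistic regression that ignores follow-up time, with no stated coding for participants who leave early

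*SAP*

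**What the plan says.** SAP 2.6.1.1 (Progression-free survival) treats the composite in two parts.

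- **Time to event.** Kaplan-Meier estimates at the end of the treatment epoch, "along with 80% two-sided confidence intervals using Greenwood's formula, will be provided if sufficient data is available", and a plot. No log-rank test, Cox model, hazard ratio or between-arm difference is named.
- **Progression rate.** The event rates of the composite and of each component, FVC decline of at least 10% included, "will be compared using logistic regression model if enough the data allows".

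That paragraph gives no time at which the binary outcome is fixed, no offset or exposure term, and no rule for incomplete follow-up. The only nearby rule is SAP 2.6.3: "Missing data will not be imputed". Planned follow-up is "a treatment period of 26 weeks (Day 1 to Day 183)".

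The protocol was narrower. Section 12.5.1 planned "the Kaplan-Meier estimates of the proportion of participants with the composite endpoint" for the composite. It kept logistic regression for the separate yes/no endpoint of FVC decline at the end of the treatment epoch, which "will be assessed using logistic regression model with absolute decline" as the dependent variable. SAP section 4, which lists departures from the protocol, does not mention that logistic regression now also covers the composite and its other components.

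**The concern.** A logistic regression of event yes/no gives every participant the same exposure. That is harmless if everyone is observed for 26 weeks, or if incomplete follow-up is alike in the two arms. It is not harmless if more participants leave the study in one arm. Their unobserved weeks must then either be counted as event-free or removed from the denominator, and each choice moves the odds ratio away from 1 even when treatment does nothing.

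The Kaplan-Meier estimates handle censoring, but no contrast between arms is planned from them. The one between-arm number a reader will have for progression is therefore the one exposed to this bias, and its direction depends on a coding that the SAP leaves open.

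**Working it through.** **What the documents supply.** Protocol 17.1.11.1 gives 47 randomized per arm and 15% drop-off (47 × 0.85 = 39.95, the 40 per group in Table 17-5). It gives no drop-out by arm. Protocol 12.8.2 gives no sizing for secondary endpoints, so the plan has no figure for the composite to reproduce. The 26-week risks (15–35%) and the arm-specific drop-out below are assumptions.

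**Model.** Event and drop-out times are exponential and independent. For 26-week risk p and drop-out d, let a = −ln(1−p) and b = −ln(1−d).

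- Observed event proportion: E = a/(a+b) × [1 − (1−p)(1−d)]
- Event-free completers: C = (1−p)(1−d)
- Odds if leavers are non-events: E/(1−E)
- Odds if event-free leavers are excluded: E/C

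**Worked case: p = 25% in both arms, drop-out 20% active, 10% placebo.**

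- Active: a = 0.288, b = 0.223, E = 0.563 × 0.400 = 0.225, C = 0.600
- Placebo: a = 0.288, b = 0.105, E = 0.732 × 0.325 = 0.238, C = 0.675
- Leavers as non-events: (0.225/0.775)/(0.238/0.762) = 0.93
- Leavers excluded: (0.225/0.600)/(0.238/0.675) = 1.07 (from unrounded E)

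**Odds ratio, active vs placebo, with no true effect (risks 15%, 25%, 35%):**

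| Drop-out active/placebo | Leavers as non-events | Leavers excluded |
|---|---|---|
| 15%/15% | 1.00, 1.00, 1.00 | 1.00, 1.00, 1.00 |
| 20%/10% | 0.94, 0.93, 0.92 | 1.06, 1.07, 1.07 |
| 25%/5% | 0.88, 0.87, 0.85 | 1.13, 1.14, 1.14 |
| 30%/5% | 0.85, 0.83, 0.82 | 1.18, 1.18, 1.18 |
| 40%/10% | 0.81, 0.79, 0.77 | 1.24, 1.25, 1.26 |

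Timing matters too. At 25% risk with 25%/5% drop-out all at week 4, non-event coding gives 0.78 rather than 0.87.

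**Rejection rate with no true effect**, two-sided 10% level, 25% risk, 47 per arm, 20,000 simulated trials:

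| Drop-out active/placebo | Log-rank | Logistic, non-events | Logistic, excluded |
|---|---|---|---|
| 15%/15% | 10.3% | 10.4% | 10.6% |
| 25%/5% | 10.2% | 11.5% | 11.6% |
| 40%/5% | 10.5% | 15.5% | 14.5% |

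**Truncation equal in both arms** (25% risk; 0, 20% or 40% of participants cut off uniformly over the 26 weeks). The odds ratio is 1.00 under no effect. With a hazard ratio of 0.6 it is 0.565, 0.571 and 0.577, so equal truncation barely matters.

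**The case against.** Three stronger readings are tempting, and the documents support none of them.

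- **That the active arm gains a spurious benefit.** This needs early leavers coded as non-events. SAP 2.1.1 ends the on-treatment period at the last treatment visit attended, which may suggest that coding, but the SAP never states it. The no-imputation rule fits exclusion at least as well, and exclusion reverses the bias.
- **That stopping the drug for tolerability truncates follow-up.** Protocol 9.1.1 keeps participants who stop treatment on their remaining visits through Day 183. Only leaving the study shortens follow-up. Protocol 9.1.2 then asks for an early end-of-treatment visit within 4 weeks, which can still record an FVC event. Death and transplant are events, not drop-out.
- **That early termination itself creates the bias.** Protocol 9.5 says, for the case that termination becomes necessary, that "participants must be seen as soon as possible for an EOT visit". The SAP does not say that Cohort 1 follow-up was cut. Had it been, sponsor termination under 1:1 randomization should affect both arms alike, and that gives an odds ratio of 1.00 under no effect.

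It is also fair to say that no arm difference in drop-out is documented. A 20%/10% split, which averages the planned 15%, moves the odds ratio only to about 0.93 or 1.07. The endpoint is secondary, the study is exploratory, no decision rule uses this result, and the regression is conditional on data.

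These points limit the size and remove any claim about direction. They do not supply a comparison that is valid when study discontinuation is unequal, or a coding rule.

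**Conclusion.** The point holds as a conditional weakness that should be corrected. The composite is a time-to-event endpoint, and its only named between-arm analysis ignores time. Under unequal study discontinuation both plausible codings distort the odds ratio, in opposite directions. The distortion is modest at mild imbalance and material at 40%/10%. There is none when drop-out is equal.

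These sizes rest on assumed risks, assumed drop-out by arm, constant hazards, and drop-out unrelated to progression. If sicker participants leave, censoring does not cure that either. The advantage of a time-to-event comparison is narrower: it uses the follow-up that was observed. It kept its nominal level in each scenario simulated and matched the logistic test when drop-out was balanced.

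**What to change.** In SAP 2.6.1.1:

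1. Make the between-arm comparison of the composite a log-rank test or Cox model stratified by standard of care. Report the hazard ratio with an 80% confidence interval, the Kaplan-Meier difference at Day 183 with its interval, or both.
2. State the censoring rule: event-free leavers are censored at last FVC assessment or last contact.
3. Keep the protocol's logistic regression for FVC decline of at least 10%, which is an endpoint in its own right, and state how early leavers are coded. If a logistic analysis of the composite stays, make it supportive with the same stated coding.
4. Label any time-to-event analysis of a non-fatal component as cause-specific, censored at death.
5. List the change from the protocol in SAP section 4.

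The cost is one SAP paragraph and standard procedures on data already collected. The downside is that a hazard ratio assumes roughly proportional hazards; the Kaplan-Meier difference at Day 183 does not.
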